### **8.9.3. Safety Phone Calls**

A safety phone call is a telephone call made to the participant by trained site personnel. This call will follow a script, which will facilitate the collection of relevant safety information. The participant will be interviewed according to the script, and information relating to MAAEs, SAEs, and concomitant medications associated with these events; receipt of non-study vaccinations and AEs leading to study withdrawal will be collected.

Participants will have 6 safety phone calls on Day 112, Day 140, Day 224, Day 252, Day 280, and Day 308 to collect MAAEs, SAEs, concomitant medications associated with these events, receipt of non-study vaccinations, and AEs leading to withdrawal.

Participants who miss the second vaccination for any reason and are expected to receive the third vaccination will have safety calls at Visit 6 (Month 3), Visit 7 (Month 4), and Visit 8 (Month 5). They should follow the same script as the other safety calls performed during the study.

All scheduled study visits should be completed within the defined visit window. In the event the participant is not able to come on site for a clinic visit as a result of the COVID-19 pandemic (self-quarantine or disruption of clinical site activities following business continuity plans and/or local government mandates for “stay at home” or “shelter in place”), a safety call to the subject should be made in place of the clinic visit. The safety call should encompass all scheduled visit assessments that can be completed remotely, such as assessment for AEs and concomitant medications (eg, as defined in scheduled safety calls at Visits 12-15). Home visits will be permitted for all non-dosing visits in the event a participant cannot make it to the clinic as a result of the COVID-19 pandemic. Home visits must be permitted by the site IRB and the subject via informed consent and have prior approval from the Sponsor (or its designee).

All safety information described by the participant must be written down in a designated location within the source documents and not written on the script used for the telephone call.

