## **Criteria for Evaluation:**

### **Safety Assessments**

1. Solicited local (injection site pain, erythema [redness], and swelling/induration [hardness]; and localized axillary swelling or tenderness ipsilateral to the vaccination arm) and systemic (headache, fatigue, myalgia [muscle aches all over the body], arthralgia [aching in several joints], nausea/vomiting, rash, fever, and chills) ARs occurring during the 7 days following each vaccination (ie, the day of vaccination and 6 subsequent days). Solicited ARs will be recorded daily using electronic diaries (eDiary).
2. Unsolicited AEs observed or reported during the 28 days following each vaccination (ie, the day of vaccination and 27 subsequent days). Unsolicited AEs are AEs that are not included as part of the protocol-defined solicited ARs. Unsolicited AEs will be collected during follow-up visits and follow-up safety calls.
3. Laboratory test abnormalities at Day 1, Day 8, Day 29, Day 56, Day 63, Day 84, Day 168, Day 175, and Day 196.
4. MAAEs from Day 1 through Day 336 (or through 6 months after last study vaccination).
5. SAEs from time of informed consent through the end of the study (Day 504).

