### 1.3. Schedule of Assessments

**Table 1: Schedule of Events for Participants Completing all Vaccinations**

Visit Number	0 	1	2	3	4 	5	6	7-8	9	10	11	12-15	16	17
Month Timepoint		M0		M1	M2		M3	M4-5	M6		M7	M8-11	M12	M18
Type of Visit	C	C	C	C	C	C	C	SC	C	C	C	SC	C	C
Study Visit Day	Part 1 D-27 to D0 (Screening) Part 2 SN D-27 to D0 SP D-41 to D0	D1 (Baseline)	D8	D29	D56	D63	D84	D112 D140	D168	D175	D196	D224 D252 D280 D308	D336	D504
Window Allowance (Days)		-	+3	± 7	± 7 	+3	-7 to +21	± 7	± 7	+3	± 7	± 7	± 7	± 7
Days Since Most Recent Vaccination (except M6/D168 visit should be based on D1)	-	0	7	28	55/0	7	28	56, 84	167/ 0	7	28	56, 84, 112, 140	168	336
ICF, demographics, inclusion/exclusion criteria, concomitant medications, non-study vaccinations, medical history 	X													
Physical examination 	X	X	X	X	X	X	X		X	X	X		X	
Vital signs 	X	X	X	X	X	X	X		X	X	X		X	
Pregnancy testing 	X	X			X				X					
Randomization		X												
Blood for Screening/safety labs 	X	X	X	X	X	X	X		X	X	X			
Blood for antibody-mediated immunogenicity 		X		X	X		X		X		X		X	X
Blood for cell-mediated immunogenicity 		X	X		X	X			X	X			X	X

Visit Number	0 	1	2	3	4 	5	6	7-8	9	10	11	12-15	16	17
Month Timepoint		M0		M1	M2		M3	M4-5	M6		M7	M8-11	M12	M18
Type of Visit	C	C	C	C	C	C	C	SC	C	C	C	SC	C	C
Study Visit Day	Part 1 D-27 to D0 (Serological) Part 2 SN D-27 to D0 SP D-41 to D0	D1 (Baseline)	D8	D29	D56	D63	D84	D112 D140	D168	D175	D196	D224 D252 D280 D308	D336	D504
Window Allowance (Days)		-	+3	± 7	± 7 	+3	-7 to +21	± 7	± 7	+3	± 7	± 7	± 7	± 7
Days Since Most Recent Vaccination (except M6/D168 visit should be based on D1)	-	0	7	28	55/0	7	28	56, 84	167/ 0	7	28	56, 84, 112, 140	168	336
Study vaccination (including 60-minute post-dosing observation period)		X			X				X					
eDiary activation for recording solicited ARs (7 days) 		X			X				X					
Review of eDiary			X			X				X				
Follow-up safety calls 								X				X		
Recording of unsolicited AEs		X	X	X	X	X	X		X	X	X			
Recording of concomitant medications and non- study vaccinations 		X	X	X	X	X	X	X 	X	X	X	X 	X 	X 
Recording of MAAEs and concomitant medications relevant to or for the treatment of the MAAE 		X	X	X	X	X	X	X	X	X	X	X	X	

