- Chemistry: AST, ALT, total bilirubin, creatinine
- Coagulation: PTT and PT

-  Sample must be collected prior to dosing on days of vaccination (Day 1, Day 56, and Day 168).
-  eDiary entries will be recorded by the participant at approximately 1 hour after vaccination while at the clinic with instruction provided by study staff. Study participants will continue to record in the diary each day after they leave the clinic, preferably in the evening, on the day of vaccination and for 6 days following vaccination. Any solicited AR that is ongoing beyond Day 7 will be reported until resolution. Adverse reactions recorded in eDiaries beyond Day 7 should be reviewed either via phone call or at the following study visit.
-  Trained study personnel will call all participants to collect information relating to any MAAEs, AEs leading to study discontinuation, SAEs, information on concomitant medications associated with those events, and any vaccinations.
-  All non-study vaccinations administered during the period starting  $\leq 28$  days before the first dose of study vaccine, and all concomitant medications and non-study vaccinations through 28 days after each vaccination will be recorded; COVID-19 vaccination (regardless of type of vaccine) will be recorded anytime from Day 1 through the End of the Study (Day 504); all concomitant medications relevant to or for the treatment of an SAE will be recorded from Screening through the End of Study (Day 504), and all concomitant medications relevant to or for the treatment of a MAAE will be recorded from Visit 1 (Day 1) through Day 336.
-  Blood for exploratory cell-mediated immunogenicity will be collected for a subset of up to 16 participants (approximately 8 CMV-seropositive and 8 CMV-seronegative) for each dose level. The Sponsor will allocate clinical sites to enroll participants in this subset. Participants engaging in blood sampling for cell-mediated immunogenicity should be advised to refrain from blood donation through the vaccination period (Day 1 through Month 7).

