-  All scheduled study visits should be completed within the defined visit window. Timing of Dose 3 is calculated in relation to Dose 1 (Day 1) and should not shift later than 167 days ( $\pm 7$  days) after Day 1; succeeding follow-up visits (Visits 10-17) are scheduled in relation to Dose 3. In the event the participant is not able to come on site for a clinic visit as a result of the COVID-19 pandemic (self-quarantine or disruption of clinical site activities following business continuity plans and/or local government mandates for “stay at home” or “shelter in place”), a safety call to the participant should be made in place of the clinic visit. The safety call should encompass all scheduled visit assessments that can be completed remotely, such as assessment for AEs and concomitant medications (eg, as defined in scheduled safety calls at Visits 12-15). Home visits will be permitted for all non-dosing visits in the event a participant cannot make it to the clinic as a result of the COVID-19 pandemic. Home visits must be permitted by the site IRB and the participant via informed consent and have prior approval from the Sponsor (or its designee).

-  In the event the visit for Dose 2 is disrupted and cannot be completed at Day 56  $\pm$  7 days as a result of the COVID-19 pandemic (COVID-19 vaccination under the FDA EUA or FDA approval, self-quarantine or disruption of clinical site activities following business continuity plans and/or local government mandates for “stay at home” or “shelter in place”), the window may be extended to Day 56 + 56 days (i.e., to 4 -months). When the extended window is utilized, the Day 84 visit is to be completed at 28 (-7 to +21) days after Dose 2 and monthly safety calls should occur every 28 days  $\pm$  7 days until the Month 6 visit (Day 168) for Dose 3. Dose 3 timing should continue to be based on Dose 1 and should not be adjusted if Dose 2 occurs in the extended dosing window (Dose 3 should not shift later than 167 days [ $\pm$  7 days] after Day 1); succeeding follow-up visits (Visits 10-17) are scheduled in relation to Dose 3.
-  Only documentation of COVID-19 vaccine is required.
-  Upon completion of final study procedures, including the final assessment and recording of MAAEs and SAEs, the participant’s treatment assignment may be unblinded via the IRT system.

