#### **3.2. Endpoints**

##### **3.2.1. Primary Endpoints**

- Solicited local and systemic ARs through 7 days after each vaccination.
- Unsolicited AEs through 28 days after each vaccination.
- Medically-attended adverse events (MAAEs) through 6 months after the last vaccination, and serious adverse events (SAEs) throughout the entire study period.

- Geometric mean titer (GMT) of serum neutralizing anti-CMV antibodies against epithelial cell infection and against fibroblast infection, and associated geometric mean ratio (GMR) of post-baseline/baseline titers at each timepoint.
- Proportion of participants with  $\geq 2$ -fold, 3-fold, and 4-fold increases in nAb over baseline against epithelial cell infection and against fibroblast infection at each timepoint.

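### The protocol contradicts itself on whether safety calls collect unsolicited AEs; if the schedule is followed, up to 6 of the 28 days after the last dose have no scheduled ascertainment

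*Protocol*

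**What the plan says.** - **Endpoint.** Protocol Section 3.2.1 lists "Unsolicited AEs through 28 days after each vaccination" as primary. The Synopsis (Safety Assessments, item 2) counts this as the vaccination day plus 27 days.
- **Synopsis on collection.** The same item states: "Unsolicited AEs will be collected during follow-up visits and follow-up safety calls".
- **Schedule.** In Table 1 the row "Recording of unsolicited AEs" is marked at Visits 1 to 6 and 9 to 11. It is blank at the calls (Visits 7-8 and 12-15) and at Visits 16 and 17.
- **Call content.** Section 8.9.3 describes scripted calls, made "to collect MAAEs, SAEs, concomitant medications associated with these events, receipt of non-study vaccinations, and AEs leading to withdrawal". Table 1 footnote 10 gives a matching list: "Trained study personnel will call all participants to collect information relating to any MAAEs, AEs leading to study discontinuation, SAEs", plus related medications and vaccinations. Footnote 9 of Tables 6 and 7 is worded alike. None of these lists includes unsolicited AEs in general.
- **Timing.** Visit 11 (Day 196) is nominally 28 days after Dose 3, with ±7 days allowed. Footnote 13 ties it to that dose: "succeeding follow-up visits (Visits 10-17) are scheduled in relation to Dose 3".
- **Early stoppers.** In Table 6 the last marked visit is Day 84 (-7 to +21 days). In Table 7 it is Day 29 (±7 days). Calls and unmarked clinic visits follow.
- **Analysis.** SAP Section 6.1 fixes a stage of 28 days after each vaccination. Section 6.3.1 uses the whole Safety Set group as denominator. Neither adjusts for the date of the closing visit.

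**The concern.** A visit meant to close a 28-day window can take place before the window ends. That is harmless if a later contact asks about the remaining days. After Doses 1 and 2, three-dose participants have a later visit that records unsolicited AEs. After the last dose they do not, unless the calls ask, and the protocol gives two answers on that.

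Sites work from the schedule and the call script. If those follow Section 8.9.3, a participant seen on post-dose day 21 who then has a minor AE on day 24, and neither seeks care nor mentions it, is counted as event-free over the full 28 days. If sites follow the Synopsis, the same event is recorded. So the ambiguity decides which primary-endpoint events enter the database, and ascertainment differs by dose number in the SAP's tables.

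**Working it through.** **Convention.** The day of vaccination is post-dose day 0, so the window is days 0 to 27. A visit is taken to cover every day up to and including its own.

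**Earliest closing visit (visit tables)**
- Dose 3, Table 1: 196 - 168 = 28 days; earliest 28 - 7 = 21, latest 35.
- Dose 2 only, Table 6: 84 - 56 = 28 days; earliest 21, latest 28 + 21 = 49.
- Dose 1 only, Table 7: the table itself gives 28 days since vaccination; earliest 21, latest 35.

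**Days left after an early visit.** A visit k days early falls on day 28 - k and leaves 27 - (28 - k) = k - 1 days. For k = 1 to 7 this is 0, 1, 2, 3, 4, 5, 6. The maximum is days 22 to 27: 6/28 = 21.4% of the window.

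**Average loss (assumption: each permitted visit day equally likely)**
- ±7 days (Table 1 Visit 11 and Table 7 Visit 3): 15 offsets, total loss 0+1+2+3+4+5+6 = 21 days; 21/15 = 1.4 days; 1.4/28 = 5.0%. Nine of the 15 offsets (-1 to +7) lose nothing.
- -7 to +21 days (Table 6 Visit 6): 29 offsets, the same total of 21; 21/29 = 0.72 days; 0.72/28 = 2.6%.

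**Next contact after the window closes on day 27**
- Dose 1, three-dose schedule: Visit 4, nominally 55 days after the dose, records unsolicited AEs. The tail is recovered.
- Dose 2, three-dose schedule: Visit 9, nominally 168 - 56 = 112 days after the dose, records them. The tail is recovered, but 112 - 27 = 85 days after closure.
- Dose 3: Visit 12 is a call at 224 - 168 = 56 ± 7, so 49 to 63 days after the dose and 22 to 36 days after closure. Its row is blank.
- Table 6: Visit 7 is a call at 112 - 56 = 56 ± 7 days, the same interval. Its row is blank.
- Table 7: Visit 4 is a call at 55 ± 7 days, 21 to 35 days after closure. Its row is blank.

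**The plan's own safety figures.** Protocol Section 9.5 gives the chance of seeing at least one participant with an AE of 2% incidence as > 95% (n = 189) and > 90% (n = 150). These reproduce: 1 - 0.98^189 = 0.978 and 1 - 0.98^150 = 0.952.

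As a stress test, assume that everyone attends Visit 11 on day 21, onset is uniform and nothing is picked up later.
- Risk spread over three windows: capture is 78/84, the effective rate is 1.86%, and the probabilities are 0.971 and 0.940.
- All risk after Dose 3: capture is 22/28, the effective rate is 1.57%, and the probabilities are 0.9499 and 0.907.

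Even the extreme case only brings the first figure to its stated bound, so the sample-size statement is not in question.

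**The case against.** The strongest reply is that the protocol does require collection. Besides the Synopsis, Section 8.9.1.3 says unsolicited AEs are captured through 28 days after each dose and that new safety information reported at calls is documented. Section 8.9.3 refers to AE assessment as defined for the calls at Visits 12-15. The SAP treats unsolicited AEs as collected throughout the study and defines a follow-up stage for them. The script itself is not in the documents. A reader might infer from Table 1 that the tail is never ascertained; these passages do not allow that conclusion.

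They do not settle the matter either. The capture statement names no contact after Visit 11. The documentation rule covers what is reported, not what is asked. The Visits 12-15 remark concerns calls replacing clinic visits during the pandemic and points back to the same calls. Table 1 also leans towards the restricted reading: concomitant medications are due through 28 days after each dose, yet footnote 15 asks only for COVID-19 vaccination at Visits 12-15.

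Two limits on size stand. MAAEs, SAEs and AEs leading to withdrawal are collected at calls on either reading, and MAAE is broad, since it includes unscheduled study-clinic visits. A reader might also take the worst case as typical. With a constant hazard, a true 28-day rate of 20% (an assumed figure) would be recorded as 1 - 0.8^(22/28) = 16%. That applies only to participants seen exactly on day 21, and only if no tail event is collected by another route.

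Finally, a reader might infer biased comparisons between groups. All arms and dose levels share the same windows and calls under an observer-blind design, and there is no hypothesis testing. Nothing in the documents shows that early attendance differs by arm.

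**Conclusion.** The contradiction is real and bears on a primary endpoint: the Synopsis stands against Table 1, its footnote 10 and Section 8.9.3. On the schedule's reading, up to 6 of 28 days after the last dose lack scheduled ascertainment of AEs that are non-serious, not medically attended and do not lead to withdrawal. This applies after Dose 3 in Table 1, after Dose 2 in Table 6 and after Dose 1 in Table 7.

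The expected effect is modest under-counting: about 1.4 days (5%) for a ±7-day closing visit and 0.7 days (2.6%) for Table 6. Both averages assume evenly spread visits and a restricted script. On that basis ascertainment differs by dose number: the tail is recovered for Dose 1, recovered with long recall for Dose 2, and not scheduled for Dose 3. Between-arm bias is not shown. The passages should be reconciled.

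**What to change.** 1. **Align the text with the Synopsis.** Amend Section 8.9.3, Table 1 footnote 10 and footnote 9 of Tables 6 and 7 so that the first call after the last dose's window asks about any AE with onset through 27 days after that dose and not already reported. The calls are Table 1 Visit 12, Table 6 Visit 7 and Table 7 Visit 4. Mark them in the unsolicited-AE rows. Optionally add Table 1 Visit 7 to shorten recall after Dose 2.
2. **For participants already past the call,** report in the CSR, by dose and group, how many closing visits fell before post-dose day 27, and state the limitation. Recorded visit dates are enough. SAP Section 6.5 says all Part 1 and Part 2 participants had completed seven months of assessments at interim analyses with cutoffs of 16 Sep 2020 and 18 Feb 2022. This step is therefore likely to be the operative one for the final analysis.

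**Cost.** One question in calls that already take place, a wording amendment and one CSR tabulation; no new visit or sample. Recorded AE rates may rise slightly, and the added reports would rest on about three to five weeks' recall after the window closes.

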#### **8.9.4. Assessment of Intensity**

An event is defined as “serious” when it meets at least one of the predefined outcomes as described in the definition of an SAE ([Section 8.9.1.2](#)), NOT when it is rated as severe.

The severity (or intensity) of an AR or AE refers to the extent to which it affects the participant’s daily activities. The Toxicity Grading Scale for Healthy Adult and Adolescent Volunteers Enrolled in Preventative Vaccine Clinical Trials ([DHHS 2007](#)) will be used to categorize local and systemic solicited ARs (per [Table 3](#)), clinical laboratory test results, and vital sign measurements observed during this study. Specific criteria for clinical and laboratory abnormalities are presented in [Appendix 3](#) and will be graded if outside of the reference range for the laboratory utilized.

The determination of severity for all unsolicited AEs should be made by the Investigator based upon medical judgment and the definitions of severity as follows:

- Mild: These events do not interfere with the participant’s daily activities.
- Moderate: These events cause some interference with the participant’s daily activities and require limited or no medical intervention.
- Severe: These events prevent the participant’s daily activity and require intensive therapeutic intervention.

Changes in the severity of an AE should be documented in the participant’s source documentation to allow an assessment of the duration of the event at each level of intensity to be performed. An AE characterized as intermittent requires documentation of onset and duration of each episode. An

AE that fluctuates in severity during the course of the event is reported once in the eCRF at the highest severity observed.

#### **8.9.5. Assessment of Causality**

The causality assessment between the AE and study vaccine exposure is one of the criteria used when determining regulatory reporting requirements. For each AE, the Investigator determines whether there is a reasonable possibility that the AE may have been caused by the study vaccine according to the categories below:

**Not Related:** There is no suspicion of a causal relationship between study vaccine exposure and the AE.

**Related:** There is reasonable possibility that there is a causal relationship between study vaccine exposure and the AE.

A “reasonable possibility” of a relationship conveys that there are facts, evidence, and/or arguments to suggest a causal relationship, rather than a relationship cannot be ruled out.

- The Investigator is obligated and will use clinical judgment to assess the relationship between mRNA-1647 vaccine and each occurrence of each AE, even if there is only limited information at the time.
- Alternative causes, such as underlying disease(s), concomitant medications or therapy, temporal relationship of the event to study vaccine administration, and other risk factors, will be considered and investigated.
- The Investigator can reference the IB in his/her assessment.
- For each AE/SAE, the Investigator must document in the medical notes that he/she has reviewed the AE/SAE and has provided an assessment of causality.
- All solicited ARs (local and systemic) will be considered causally related to vaccination.
- There may be situations in which an SAE has occurred, and the Investigator has minimal information to include in the initial report to the Sponsor. However, it is very important that the Investigator always make an assessment of causality for every event before the initial transmission of the SAE data to the Sponsor.

The Investigator may change his/her opinion of causality in light of follow-up information and send an SAE follow-up report with the updated causality assessment.

#### **8.9.6. Reporting of Serious Adverse Events**

The following process for reporting an SAE ensures compliance with 21 CFR 312 and ICH guidelines. After learning that a participant has experienced an SAE, the Investigator or designee is responsible for reporting the SAE to the Sponsor, regardless of relationship, within 24 hours of becoming aware of the event via the EDC system.

It is the Principal Investigator's responsibility to notify the IRB of all SAEs that occur at his or her site. Investigators will be notified of all unexpected, serious, vaccine-related events (7- and 15-day Safety Reports) that occur during the clinical trial. Each site is responsible for notifying its IRB of these additional SAEs.

The Sponsor is responsible for notifying the relevant regulatory authorities of certain events in accordance with the regulations for each country.

The Sponsor will provide the SMC and the IST with data of all SAEs on an ongoing basis.

